- 15 Cardiac surgery or non-elective percutaneous coronary interventions (PCI/TAVI) (within 3 months) or open chest coronary artery bypass grafting or valvular repair/replacement (within 3 months) prior to screening or is planned to undergo any of these procedures after randomisation.
- 16 Heart transplantation or left ventricular assist device at any time.
- 17 Kidney or any organ transplantation.
- 18 History or ongoing allergy/hypersensitivity, as judged by the investigator, to SGLT2i (eg, dapagliflozin, canagliflozin, empagliflozin) or drugs with a similar chemical structure to zibotentan.
- 19 Any clinically significant disease or disorder (eg, cardiovascular, gastrointestinal, liver, renal, neurological, musculoskeletal, endocrine, metabolic, psychiatric, major physical impairment) which, as judged by the investigator, might put the participant at risk because of participation in the study, or probable alternative primary reason for participant's symptoms in judgment of investigator, including but not limited to:
 - (a) Isolated pulmonary arterial hypertension (defined as mean PAP \geq 25 mmHg at rest) or right ventricular failure; in the absence of left-sided HF.
 - (b) Anaemia defined as haemoglobin (Hb) level $<$ 100 g/L or 10 g/dL at screening (Visit 1).
 - (c) Severe chronic obstructive pulmonary disease (COPD) or other lung disease including but not limited to pulmonary fibrosis requiring chronic O₂ therapy, regular nebuliser use, or oral steroid therapy.
- 20 Stroke, transient ischemic attack, carotid surgery, or carotid angioplasty within previous 3 months prior to screening.
- 21 Active malignancy requiring treatment (except for basal cell or squamous cell carcinomas of the skin) and malignancies 5 years prior to screening.
- 22 Severe hepatic impairment (Child-Pugh class C Hepatic impairment), aspartate transaminase [AST] or alanine transaminase [ALT] $>$ 2x the upper limit of normal [ULN]; or total bilirubin $>$ 2x ULN at time of screening. An isolated increase in bilirubin in participants with known Gilbert's syndrome is not a reason for exclusion.
- 23 Participants with newly detected pathological laboratory values or an ongoing disease condition requiring investigation and/or initiation or adjustment of current treatment (in the opinion of the investigator).
- 24 Drug or alcohol abuse, either current or within 12 months before screening.
- 25 Positive hepatitis C antibody or hepatitis B virus surface antigen at screening.

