If an unexpected, acute decline in kidney function is observed, the participant should be promptly evaluated. Volume depletion, hypotension, intercurrent medical problems and concomitant drugs may cause increases in blood creatinine. Urinary tract infection and urinary obstruction should be considered. Several drugs may cause a decline in kidney function, especially non-steroidal anti-inflammatory drugs and certain antibiotics such as trimethoprim. If any drug is suspected of causing or contributing to worsening kidney function, their use should be reconsidered.
- More than 3% increase in weight (at least 2.5% must be from total body water as measured by bioimpedance) from start of treatment (Day 1).
- Heart failure.

Note that discontinuation from study intervention is NOT the same thing as a withdrawal from the study.

If study interventions are permanently discontinued, the participant will continue with the study visits and complete further evaluations as per the SoA (Table 1).

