Appendix E Actions Required in Cases of Increases in Liver Biochemistry and Evaluation of Hy's Law

E 1 Introduction

This Appendix describes the process to be followed in order to identify and appropriately report Potential Hy's Law (PHL) cases and Hy's Law (HL) cases. It is not intended to be a comprehensive guide to the management of elevated liver biochemistries.

During the course of the study the investigator will remain vigilant for increases in liver biochemistry. The investigator is responsible for determining whether a participant meets potential PHL criteria at any point during the study.

All sources of laboratory data are appropriate for the determination of PHL and HL events; this includes samples taken at scheduled study visits and other visits including central and all local laboratory evaluations even if collected outside of the study visits; for example, PHL criteria could be met by an elevated ALT from a central laboratory **and/or** elevated TBL from a local laboratory.

The investigator will also review Adverse Event data (for example, for AEs that may indicate elevations in liver biochemistry) for possible PHL events.

The investigator participates, together with AstraZeneca clinical project representatives, in review and assessment of cases meeting PHL criteria to agree whether Hy's Law (HL) criteria are met. HL criteria are met if there is no alternative explanation for the elevations in liver biochemistry other than Drug Induced Liver Injury (DILI) caused by the Investigational Medicinal Product (IMP).

The investigator is responsible for recording data pertaining to PHL/HL cases and for reporting SAEs and AEs according to the outcome of the review and assessment in line with standard safety reporting processes.

E 2 Definitions

Potential Hy's Law

Aspartate Aminotransferase (AST) or Alanine Aminotransferase (ALT) $\geq 3 \times$ Upper Limit of Normal (ULN) **together with** Total Bilirubin (TBL) $\geq 2 \times$ ULN at any point during the study following the start of investigational product irrespective of an increase in Alkaline Phosphatase (ALP).

Hy's Law

AST or ALT $\geq 3 \times$ ULN **together with** TBL $\geq 2 \times$ ULN, where no other reason, other than the IMP, can be found to explain the combination of increases, eg, elevated ALP indicating cholestasis, viral hepatitis, another drug.

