For PHL and HL the elevation in transaminases must precede or be coincident with (ie, on the same day) the elevation in TBL, but there is no specified timeframe within which the elevations in transaminases and TBL must occur.

E 3 Identification of Potential Hy's Law Cases

In order to identify cases of PHL it is important to perform a comprehensive review of laboratory data for any participant who meets any of the following identification criteria in isolation or in combination:

- $ALT \geq 3 \times ULN$.
- $AST \geq 3 \times ULN$.
- $TBL \geq 2 \times ULN$.

Central Laboratories Being Used:

When a participant meets any of the PHL identification criteria, in isolation or in combination, the central laboratory will immediately send an alert to the investigator (also sent to AstraZeneca representative).

The investigator will also remain vigilant for any local laboratory reports where the PHL identification criteria are met, where this is the case the investigator will:

- Notify the AstraZeneca representative.
- Request a repeat of the test (new blood draw) by the central laboratory without delay.
- Complete the appropriate unscheduled laboratory eCRF module(s) with the original local laboratory test result.

When the identification criteria are met from central or local laboratory results the investigator will without delay:

- Determine whether the participant meets PHL criteria (see Section E 2 for definition) by reviewing laboratory reports from all previous visits (including both central and local laboratory results).

E 4 Follow-up

E 4.1 Potential Hy's Law Criteria not met

If the participant does not meet PHL criteria the investigator will:

- Inform the AstraZeneca representative that the participant has not met PHL criteria.

- Perform follow-up on subsequent laboratory results according to the guidance provided in the CSP.

E 4.2 Potential Hy's Law Criteria met

If the participant does meet PHL criteria the investigator will:

- Notify the AstraZeneca representative who will then inform the central Study Team.
- Within 1 day of PHL criteria being met, the investigator will report the case as an SAE of Potential Hy's Law; serious criteria 'Important medical event' and causality assessment 'yes/related' according to CSP process for SAE reporting.
- For participants that met PHL criteria prior to starting IMP, the investigator is not required to submit a PHL SAE unless there is a significant change[#] in the participant's condition.

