4.11 Safety Evaluation

All safety summaries and analyses will be based upon the Safety Analysis Set as defined in Section 4.6 and the on-treatment period as defined in Section 4.2.1, unless otherwise specified. Safety summaries will be presented by treatment arm.

Change from baseline will be calculated as the difference between the post-dose value at each time point and the last non-missing value prior to or on the same date as administration of the first dose of investigational products.

Individual safety and tolerability data will be provided in data listings and summarised as appropriate by treatment and overall. Continuous variables (laboratory parameters, ECG, and vital signs) will be summarised using descriptive statistics (n, mean, SD, minimum, median, and maximum) as appropriate by scheduled assessment time point. Where applicable, data will be summarised for the observed value, and for the corresponding change from baseline/screening. Categorical variables will be summarised in frequency tables (counts and percentage) as appropriate by scheduled assessment time point.

Changes from baseline in categorical data will be summarised using shift tables where appropriate.

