4.11.4 Clinical Laboratory Evaluation

The following summaries will be provided:

- A summary, which will cover n, mean, SD, minimum, Q1, median, Q3, and maximum, of the observed values and change from baseline for all clinical chemistry (including cystatin C), haematology and quantitative urinalysis parameters by treatment arm and time point
- A summary of baseline to maximum observation on treatment in each clinical chemistry (including cystatin C) and haematology laboratory parameter by treatment arm (shift table)

- A summary of baseline to minimum observation on treatment in each clinical chemistry (including cystatin C) and haematology laboratory parameter by treatment arm (shift table)
- A plot of ALT versus total bilirubin, expressed as multiples of upper limit of normal (ULN)
- A plot of AST versus total bilirubin, expressed as multiples of ULN
- A summary of the number and percentage of participants reporting maximum on-treatment ALT and AST by maximum total bilirubin for assessing Hy's Law criteria
- A summary of individual participant data for participants with Potential Hy's Law i.e. participants with combined ALT or AST, and bilirubin elevations
- A summary of key participant information for participants with treatment-emergent changes in laboratory parameters (refers to clinical chemistry and haematology, other laboratory parameters are in supportive listings) outside of pre-defined criteria
- A summary of treatment-emergent laboratory changes (see [Appendix C: Treatment-Emergent Changes in Relevant Laboratory Parameters](#))
- A summary of baseline versus maximum value on treatment for urinalysis by treatment arm (shift table)
- A summary of treatment-emergent urinalysis changes

Treatment-emergent changes in relevant laboratory parameters outside pre-defined criteria for this study are provided in [Appendix C: Treatment-Emergent Changes in Relevant Laboratory Parameters](#). Treatment-emergent urinalysis changes are defined as: negative/trace at baseline to ++, +++, +++++ at any visit after baseline or an increase of at least ++, for example + to +++, ++ to +++++.

By-participant listings of all laboratory data will be provided including participant identifier, treatment, age, sex, race, visit, category, lab test name, result, change from baseline (where appropriate) and standard units. Laboratory reference ranges will also be listed and out of range values will be flagged.

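### The SAP's Hy's Law cross-tabulation, and by default its Potential Hy's Law summary, cover a shorter window than protocol Appendix E, and the cross-tabulation ignores the order of the rises

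*Protocol*

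**What the plan says.** Protocol Appendix E 2 defines Potential Hy's Law as a transaminase (AST or ALT) at or above 3×ULN combined with total bilirubin at or above 2×ULN, occurring "at any point during the study following the start of investigational product". It adds an order rule: "the elevation in transaminases must precede or be coincident with (ie, on the same day) the elevation in TBL". No limit is set on the gap between the two. Appendix E 1 accepts every laboratory source, "including central and all local laboratory evaluations even if collected outside of the study visits". Protocol 9.4.3.3 likewise ties Hy's Law reporting to potential cases found in the course of the study, not to time on drug.

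SAP 4.11.4 plans a count and percentage of participants "reporting maximum on-treatment ALT and AST by maximum total bilirubin", and an individual summary of Potential Hy's Law, glossed as "participants with combined ALT or AST, and bilirubin elevations". Neither item gives thresholds or an order rule, or says whether local results enter. SAP 4.11 sets the default period for safety outputs as "the on-treatment period as defined in Section 4.2.1, unless otherwise specified". Under SAP 4.2.1 that period closes 28 days after the last dose, or sooner if the participant finishes the study, is lost, or withdraws consent. No exception is stated for the Hy's Law outputs, and SAP 4.15 does not list the difference among its departures from the protocol.

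Under protocol 7.1, after permanent discontinuation of study drug "the participant will continue with the study visits and complete further evaluations as per the SoA". The Schedule of Activities has central chemistry at every visit.

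**The concern.** The two documents use one name for two different sets of participants. A case that meets Appendix E more than 28 days after last dose is reported by the site as an SAE but falls outside the period on which the Hy's Law table is built. In the other direction, a table of maxima pairs the highest transaminase with the highest bilirubin whenever each occurred, so a bilirubin rise that came first and had resolved before a later transaminase rise is counted, although Appendix E would not count it.

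Potential Hy's Law cases are rare and are read one at a time. One case is 1/166 = 0.6% of a main arm and 1/83 = 1.2% of the zibotentan 0.25 mg arm. A clinical study report whose Hy's Law table and SAE table give different counts leaves the reader to work out which is right. Any omission falls on participants who stopped drug early.

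**Working it through.** The plan states no figure on this point, so there is none to reproduce. The check compares the definitions, does date arithmetic on the visit schedule, and applies both rules to constructed laboratory courses.

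**1. Definitions compared**

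| Element | Protocol Appendix E | SAP 4.11.4 |
|---|---|---|
| Window | Whole study after first dose | On-treatment: stated for ALT/AST in the cross-tabulation; by the 4.11 default for bilirubin and for the individual summary |
| Order | Transaminase first or same day | None in the cross-tabulation; individual summary silent |
| Thresholds | 3×ULN and 2×ULN | None in 4.11.4; given in the footnote to SAP Table 3, which points to Appendix E |
| Sources | Central and local | Not stated for liver tests |

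**2. Window arithmetic**

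Inputs: post-baseline chemistry at target Days 8, 22, 43, 64, 84 and 98 (Schedule of Activities); on-treatment end = last dose day + 28 (SAP 4.2.1). A panel is outside when its day exceeds last dose day + 28, that is, when last dose day < panel day − 28.

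- Week 14: 98 − 28 = 70, so outside if last dose is before Day 70 (67 to 73 with visit windows).
- Week 12: 84 − 28 = 56 (54 to 58).
- Week 9: 64 − 28 = 36 (34 to 38).
- Week 6: 43 − 28 = 15 (13 to 17).

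Examples:

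- Last dose Day 22: window ends Day 50; Weeks 9, 12 and 14 are outside.
- Last dose Day 43: window ends Day 71; Weeks 12 and 14 are outside.
- Last dose Day 64: window ends Day 92; Week 14 is outside.

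For a completer who takes the last dose at Visit 7 and attends both visits within the protocol windows, Visit 8 falls 95 − 86 = 9 to 101 − 82 = 19 days after last dose (target 98 − 84 = 14). This is always inside 28 days.

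**3. Both rules applied to constructed courses**

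The SAP rule here borrows the Appendix E thresholds, because 4.11.4 gives none, and applies the on-treatment default to bilirubin.

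| Course | Appendix E | SAP maxima |
|---|---|---|
| Last dose Day 43; ALT 5× and bilirubin 2.5× on Day 84 | Case | Missed |
| Last dose Day 22; ALT 4× on Day 43, bilirubin 2.5× on Day 64 | Case | Missed |
| Completer; both raised on Day 98 | Case | Counted |
| Completer; ALT 4× on Day 22, bilirubin 2.5× on Day 64 | Case | Counted |
| Completer; bilirubin 2.5× on Day 8 only, ALT 4× on Day 64 | Not a case | Counted |

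The first row does not depend on how the default is read for bilirubin, because the ALT rise itself is off treatment. The second row does: if bilirubin were taken over the whole study, that participant would be counted.

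**4. Scale**

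The documents give no rate of stopping drug before Day 70 with continued attendance. As an assumption, 2% to 15% of the 415 would be 415 × 0.02 = 8 to 415 × 0.15 = 62 participants with at least one panel outside the window. These are participants with excluded panels, not Potential Hy's Law cases, of which there may be none.

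**The case against.** **Different purposes.** Appendix E is a procedure by which sites identify and report cases. The cross-tabulation is a screening display, and a uniform 28-day safety window is a legitimate convention. This stands as a defence of keeping the table. It does not explain why the summary that carries the protocol's own term should follow a different window without saying so.

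**The individual summary may be right already.** Its item does not say on-treatment, and the SAP Table 3 footnote sends the reader to Appendix E, so a programmer could apply the full definition. This partly stands: the limit on that summary comes only through the Section 4.11 default, and 4.11.4 does not settle it.

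**Nothing is lost from the report.** A reader might infer that a late case would vanish. The documents do not support that. Appendix E 4.2 requires an SAE report within one day of the criteria being met, SAP 4.11.2 produces all AE tables for on treatment and for on + off treatment, and SAP 4.11.4 lists all laboratory data by participant. What remains is a possible disagreement between outputs. The SAE tables are also not a stable count of Potential Hy's Law, because Appendix E 5 has the event term, causality and seriousness reassessed when another adverse event explains the rises.

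**Gilbert's syndrome.** Exclusion criterion 22 says that "An isolated increase in bilirubin in participants with known" Gilbert's syndrome does not exclude, and a reader might infer that such participants will inflate the table. An isolated bilirubin rise never meets the transaminase threshold. If bilirubin stays raised and ALT rises later, a flag that only asks for raised bilirubin on the same or a later date would count that participant too. The order must therefore be judged on when the bilirubin elevation began. Over-counting in a screen is also the cautious direction.

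**Size.** A reader might take the SAP's 10% drop-out allowance and conclude that about 17 of 166 per main arm are affected. That allowance inflates the sample size to reach participants evaluable for UACR. It is not a rate of stopping drug early while still attending, and people who leave the study have no later panels to omit.

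**Conclusion.** The mismatch is real and limited. As written, the cross-tabulation, and through the default the individual summary, can omit an Appendix E case in a participant who stops drug before about Day 70 and keeps attending. The cross-tabulation can also count a participant whose bilirubin rise came first and had resolved. On-schedule completers are unaffected by the window.

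The conclusion rests on three things: the Section 4.11 default applies where 4.11.4 is silent; participants who stop drug early do keep attending, as protocol 7.1 provides; and visits fall near their target days. The number of cases affected cannot be estimated from the documents and may be zero. No primary or secondary endpoint is touched. The consequence is a Hy's Law table that could disagree with the SAE tables and listings in the same report.

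**What to change.** In SAP 4.11.4, derive a Potential Hy's Law flag by reference to protocol Appendix E. It should use the appendix's thresholds, all laboratory sources (scheduled, unscheduled and local), the whole study after first dose, and the order judged on the onset of the bilirubin elevation. Show participants whose bilirubin was already raised before the transaminase rise in a separate row, so that they are neither merged with cases nor hidden.

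Report n (%) by arm for on-treatment and for on + off treatment, and base the individual summary on the flag. Keep the maximum-by-maximum table and the ALT and AST plots against bilirubin, labelled as screening displays.

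The cost is slightly more programming: one derived variable and one extra column. The SAP already reports adverse events and fluid-related events for both periods, so the layout exists.

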Appendix F COVID-19 Specifics

F 1 Background to COVID-19

There is currently an outbreak of respiratory disease (COVID-19) caused by a novel SARS-CoV-2 that was first detected in Wuhan City, Hubei Province, China in 2019. This new virus has rapidly spread across the globe causing the World Health Organization to declare a pandemic situation on 12 March 2020. The countermeasures initiated by national and local governments worldwide and the recommendations issued by the health authorities have impacted current and new clinical studies. As the threat of pandemic burden including new outbreaks, locally or globally, will impact the further conduct of clinical studies, appropriate risk assessments and mitigation measures will need to be taken into consideration in all clinical studies to protect subjects, site staff, and society as a whole.

Both EMA and Food and Drug Administration (FDA) as well as national health authorities in Europe have issued new guidelines that aim to provide recommendations for actions for conduct of clinical studies of medical products during COVID-19 pandemic. Since the pandemic situation is evolving, guidelines, recommendations, national laws, and local restrictions may change at high pace. Given the circumstances of potentially relapsing pandemic or epidemic situation with regard to the spread of COVID-19 in future, special attention will be paid to protect participants in the study and site staff involved in the investigations against infection with SARS-CoV-2 as requested by the newly issued EMA guideline.

F 2 Risk Assessment for COVID-19 Pandemic

The mechanism of action of either zibotentan and/or dapagliflozin are unlikely to impact the course of infection with SARS-CoV-2. Dapagliflozin is an anti-glycaemic agent and zibotentan is an ETA receptor antagonist; neither is expected to cause immune suppression. Therefore, risk for the participants to be exposed to SARS-CoV-2 or to suffer from COVID-19 is expected to be similar to the background population with the same co-morbidities, in particular CKD. The risk of exposure to infected people cannot be completely excluded as the participants may need to be in public areas (eg, commute to the site) and have additional human contact (eg, with site staff and other participants of the clinical study).

Measures to mitigate the additional risks caused by COVID-19 are:

- This study is going to start including participants only when the sponsor and CRO in collaboration deem it is safe to start the study. In addition, the study will not start until the local confinement measures or other safety restrictions linked to the COVID-19 pandemic imposed by the local authorities are compatible with safe conduct of the study.
- Current national laws and local recommendations for prevention of pandemic will be strictly adhered to.

- Participants will be closely monitored for any signs and symptoms of COVID-19, including fever, dry cough, dyspnoea, sore throat, and fatigue throughout the study during the pandemic. Once clinical signs of infection are reported by participants, the investigator needs to determine whether samples can be collected, and safety data can be recorded on site. If not, AEs and concomitant medications will be obtained via phone calls. The decision to continue with dosing the participant with the investigational products in the event of him/her showing symptoms of COVID-19 infection will be per investigator's discretion.
- The probability of virus transmission will be controlled as much as possible by:
 - Advice for participant to adhere to local requirements for reduction of the public exposure while ambulatory.
 - Confirmation of COVID-19 infection by optional laboratory assessment will be conducted based on availability (test capacity and turnaround time) of approved tests and on investigator's discretion.
 - Requesting all participants are contacted by phone 1 day prior to every visit for assessing COVID-19 symptoms and signs and are asked not to attend the site in case of suspected reports. In addition, participants are asked for any contact with a person who has tested positive for SARS-CoV-2. If applicable, participants will be referred to the local health care system for further follow-up and treatment.
 - Physical distancing and person-to-person contact restrictions will be applied during site visits.
 - Where physical distancing is not possible, personal protective equipment will be used by study participants (surgical face mask, gloves) and staff (for example but not limited to masks, gloves, protectors, medical suits) if deemed appropriate by the investigators and site staff and guided by local requirements.
 - Logistical improvements of the site and structural measures of the study site building will be implemented to further improve physical distancing.
- If site visits are not possible due to local restrictions, home nursing visits may be considered after discussion with and approval by the sponsor.

F 3 Restrictions Related to COVID-19

During the COVID-19 pandemic, participants are advised to adhere to local requirements for reduction of the public SARS-CoV-2 exposure while ambulatory. If applicable, prior to screening (Visit 1), potential participants should be called to confirm they are not experiencing any COVID-19 symptoms and signs and are asked not to attend the site in case of suspected infection. If appropriate, participants will be referred to the local health care system. Physical distancing and person-to-person contact restrictions will be applied and explained to participants while staying at the study site. Where physical distancing is not possible, study

participants will be asked to use surgical face masks and/or gloves if deemed appropriate by the investigator and site staff and guided by local requirements.

F 4 Data Quality Assurance Related to COVID-19

Monitoring visits at site will be limited to a minimum required as deemed appropriate during COVID-19 pandemic, per local regulations.

F 5 References

Guidance on the Management of Clinical Trials during the COVID 19 (Coronavirus) pandemic, EMA, Version 3 (28/04/2020).

https://ec.europa.eu/health/sites/health/files/files/eudralex/vol-10/guidanceclinicaltrials_covid19_en.pdf

FDA Guidance on Conduct of Clinical Trials of Medical Products during COVID-19 Public Health Emergency, March 2020, Updated on July 02, 2020 <https://www.fda.gov/regulatory-information/search-fda-guidance-documents/fda-guidance-conduct-clinical-trials-medical-products-during-covid-19-public-health-emergency>

